# 6.2 Previous and concomitant medications

A previous medication / non-pharmacological therapy is any treatment for which the end date is prior to the start of study treatment.

A concomitant medication / non-pharmacological therapy is any treatment that is either ongoing at the start of study treatment or is initiated during the treatment period.

#### 6.2.1 Allowed concomitant therapy

Therapies considered necessary for the study participant's well-being and not categorized as prohibited concomitant medications can be used in this study and must be documented in the medical charts. However, initiation of a new medication is to be discouraged and any concomitant (i.e., ongoing maintenance) medication will preferably not be changed during the study.

#### 6.2.2 Forbidden concomitant therapy

Study participants must not be withdrawn from medically necessary therapies in order to participate in the study. These participants must rather be considered as non-eligible for the study due to their medical condition and their requirement for these therapies.

The following concomitant therapies are forbidden during the study:

• CNS-active drugs, such as centrally active anticholinergics, sedating antihistamines, morphine and other opioids, anticonvulsants, antidepressants, anxiolytics, mood

stabilizers, antipsychotics, stimulants, sleep drugs, and anti-Parkinson's drugs within 30 days prior to Screening or planned to be initiated during the study and until EOS.

- Medications that affect body weight or appetite, including weight-loss medications, insulin, GLP-1 receptor agonists, systemic corticosteroids etc., within 3 months prior to Screening and until EOT.
- Moderate and strong inducers and inhibitors of CPY3A4, sensitive substrates of CYP3A4, CYP2C19, CYP2C8, and CYP2C9 within 2 weeks prior to randomization (Visit 2) or planned to be initiated during the study and until 24 h after EOT.
- Any medications for the treatment of BE, including lisdexamfetamine (Vyvanse®), any other eating disorder, obesity, or weight gain, or any other medication that could result in weight gain or weight loss including over the counter and herbal products within 3 months prior to Screening.
- Psychotherapy or behavioral weight-loss interventions for BED during the study and until 24 h after EOT.

# 6.3 Medical care of study participants after study completion / withdrawal from study

After the study participant's study completion or premature withdrawal from the study, whichever applies, the investigator/delegate will explain to study participants what treatment(s) / medical care is necessary and available according to local medical practice and applicable guidelines.

Female study participants of childbearing potential will be reminded of the contraception requirements as described in Section 5.5.2.

# 7 VISIT SCHEDULE AND STUDY ASSESSMENTS AND PROCEDURES

# 7.1 General information

The treatment period starts with the administration of the first dose of study treatment and ends on the day of the last dose of study treatment (EOT). The study participants will be treated for 12 weeks.

The safety follow-up period starts on the day after the last dose of study treatment (EOT) and ends at the EOS visit.

For participants who prematurely discontinue study treatment, the EOT visit will occur within 5 days of the last intake of study treatment. For participants who complete the treatment period as planned, the Week 12 visit corresponds to the EOT visit.

The study visits and their respective time windows are listed in the schedule of activities [Table 1]. All assessments pertaining to a visit must be performed on the same day. If it is

not possible to complete all assessments on the same day, a visit may extend over more than 1 day within the allowed time window.

# 7.1.1 Screening

The study participants who agree to be part of the study and the investigator/delegate must sign the ICF prior to participation in the study. The ICF must be fully signed [see Section 10.2 for informed consent procedure] on the day of the Screening visit.

Screening starts with the signature of the ICF. The date on which the first screening assessment is performed corresponds to the date of the Screening visit. Screening assessments may be performed at any time during the screening period.

It is the responsibility of the investigator/delegate to obtain written informed consent from each participant in this study after adequate face-to-face explanation of the study objectives, design, and potential hazards of the study.

If the first study-specific procedures or assessments are performed on the day that the ICF is signed, it must be clear from the source documents that informed consent was obtained prior to any study-specific procedures being performed (i.e., time of signature must be available).

Procedures or assessments conducted as part of the study participant's routine clinical management (e.g., laboratory samples) which were obtained before signing of the ICF may be used for screening or baseline purposes provided the procedures met the protocol-specified criteria and were performed within the time frame defined in the schedule of activities [Table 1]. In such cases, it must be clear from the source documents when and for which reason the assessment was done prior to the signing of the ICF.

After the ICF has been fully signed, the investigator/delegate contacts the IRT system to get a study participant number allocated to the study participant.

It is not permitted to re-screen study participants in this study.

# 7.1.2 Unscheduled visits

Unscheduled visits may be performed at any time during the study and will be recorded in the eCRF. Depending on the reason for the unscheduled visit (e.g., AE), appropriate assessments will be performed based on the judgment of the investigator and the results will be recorded in the eCRF. After an unscheduled visit, the regular scheduled study visits must continue according to the schedule of activities [Table 1].

# 7.1.3 Study completion

A study participant who completes 12 weeks of treatment and the safety follow-up period is considered to have completed the study per protocol. A study participant who prematurely discontinues the study due to pre-defined criteria [see Section 5.9.1], withdrew from the study, was lost to follow-up, or was withdrawn from the study because of study closure or premature termination or suspension of the study [see Section 10.10] is considered as an early discontinuation.

# 7.2 Study assessments and procedures

The study assessments and procedures and their timing are summarized in the schedule of activities [Table 1].

All study assessments performed during study visits (scheduled or unscheduled) are done by the investigator/delegate and are recorded in the eCRF, unless otherwise specified.

In general, it is recommended to start visits by performing blood sample collection, so that study participants do not stay under fasted conditions too long. Questionnaires and scales are *recommended* to be performed in the following order:

# At Screening:

- SCID-5 (paper-based) to confirm diagnosis of BED
- EDE-Q (ePRO) which helps confirm diagnosis of BED and rule out bulimia nervosa
- MINI (paper-based) should ideally be done after the EDE-Q
- CGI-S (ePRO), taking into account results of all other eating disorder evaluations
- Instructions to the study participant on how to complete the BE diary (paper-based)

# At Randomization and subsequent visits:

- Review of paper-based questionnaires BE diary (and SSS)
- YBOCS-BE (ePRO)
- CGI-S (ePRO)
- Other scales can be done in order of investigator's clinical judgment

The following assessments will be analyzed by an external provider (results will be transferred to sponsor and to the investigators):

• Laboratory variables

- ECG variables
- Questionnaires completed using a touchscreen device (handheld tablet device or laptop), listed below.

If the PI delegates any study procedure/assessment for a study participant to an external facility, he/she must inform the sponsor to whom these tasks are delegated. The setup and oversight must be agreed upon with the sponsor. The supervision of any external facilities remains the responsibility of the PI.

Calibration certificates / evidence of equipment maintenance for the below-listed equipment used to perform study assessments must be available prior to the recruitment of the first study participant. Calibration certificates / evidence of equipment maintenance for other equipment must be available as per local requirements.

Equipment for which calibration certificates are needed:

- Temperature measurement devices for study treatment storage area and laboratory sample storage (e.g., freezer)
- Body-weight scale
- Use of touchscreen device
- Study participants will be required to complete the following questionnaires on a touchscreen device at the study site/clinic during the appropriate visit days [see Table 1 and Sections 7.2.3 and 7.2.4 for further description of the respective questionnaires]:
- EDE-Q, BWSQ, PGI-S, PGI-C, tasks
- Investigators, delegated physicians, specialist nurses or nurse practitioners trained according to local requirements and local clinical practice will be required to complete the following questionnaires on a touchscreen device at the site:
  - YBOCS-BE, HAMD-17, C-SSRS©, CGI-S, CGI-C
- Sites will be properly trained on the accurate use of the touchscreen device by the sponsor or an external CRO and are then expected to train their study participants on how to appropriately complete the questionnaires. Data collected from the touchscreen device will be electronically transferred to the sponsor by the CRO.
- For further details refer to the touchscreen device manual.

#### 7.2.1 Demographics / baseline characteristics

Demographic and baseline characteristics data to be collected in the eCRF for all study participants include: age, sex, race and ethnicity (if allowed in the country). Relevant medical history and/or current medical conditions, based on the investigator/delegate's judgment (e.g., chronic and ongoing acute conditions, serious past conditions including

previous surgeries), present before and/or at the time of signing of the ICF will be recorded in the eCRF. Where possible, diagnoses rather than symptoms will be recorded.

The reason for not being of childbearing potential will be recorded in the eCRF.

# 7.2.2 Reporting of previous/concomitant medications / non-pharmacological therapy / medical or surgical interventions or procedures and methods of birth control in the eCRF

A concomitant medication / non-pharmacological therapy is any treatment that is either ongoing at the start of study treatment or is initiated during the treatment period.

A previous medication / non-pharmacological therapy is any treatment for which the end date is prior to the start of study treatment.

The use of all concomitant medications / non-pharmacological therapy (including contraceptives and traditional and alternative medicines, e.g., plant-, animal-, or mineral-based medicines) will be recorded in the eCRF. Previous medications / non-pharmacological therapy must be recorded in the eCRF if discontinued less than 30 days prior to signing of the informed consent.

Any medical or surgical intervention performed on the study participant at any time during the study, will be documented in the eCRF.

The methods of birth control used (including non-pharmacological methods) by the WOCBP (and partner if applicable) must be recorded in the eCRF.

In addition, the investigator/delegate will record any change in the method of contraception in the eCRF at monthly intervals and will remind the study participant to follow the protocol-mandated method of contraception up to 30 days after study treatment discontinuation.

Note: The documentation of method of contraception can be based on the site personnel's review of the study participant's medical records, medical examination, or medical history interview of the study participant.

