### Table 1Schedule of activities

PERIODS	Name	SCREENING		TREATMENT							FOLLOW-UP	UNSCHEDULED
	Duration	2–4 weeks		12 weeks							7–13 days	NA
VISITS	Number	1	2	3	4	5	6	7	8	ЕОТ	EOS	U1
	Name	Screening	Randomization	Week 1	Week 2	Week 4	Week 6	Week 8	Week 10	Week 12 / End-of-Treatment 	End-of-Study visit	Unscheduled visit 
	Time window	Day –28 to Day –1	Day 1	Day 8 (±1)	Day 15 (±2)	Day 29 (±2)	Day 43 (±2)	Day 57 (±2)	Day 71 (±2)	Day 85 (±2) or 1 to 5 days after last dose if premature EOT	10 ± 3 days after EOT	Any day between ICF signature and EOS
Signature of I form	nformed consent	Х										
Eligibility		Х	Х									
Demographics	5	Х										
Medical histor	ry	Х										
Previous/conc	omitant therapy	Х	Х	Х	Х	Х	Х	Х	Х	Х		
Physical exam	ination	Х								Х		
Body weight a	nd height 	Х	Х	Х	Х	Х	Х	Х	Х	Х		
Vital signs (Bl	P, PR, RR, T°)	Х	Х	Х	Х	Х	Х	Х	Х	Х		(X) 
12-lead ECG (	(central)	Х								Х		(X) 
Hematology /	blood chemistry 	Х				Х		Х		Х		(X) 
Serum/urine p	oregnancy test 	Х	Х			Х		Х		Х	Х	(X) 
Thyroid funct	ion	Х										
Urine drug sc	reen	Х	Х	Х	Х	Х	Х	Х	Х	Х		
Viral serology	τ	Х										
PK sampling 						Х		Х		X		
Binge eating d	liary completion									•••••		
Stanford Slee	piness Scale 			 	 ▶							
Binge eating d	liary check		Х	X	X	X	X	X	X	Х		
YBOCS-BE			Х			X		X		Х		
PGI-S			Х			X		X		Х		

Doc No D-21.148

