# 4.1.1 Study periods for an individual study participant

The study comprises the following consecutive periods:

**Screening period:** Lasts a minimum of 14 days and up to 28 days; starts with the full signature (study participant, investigator/delegate) of the ICF and ends with the study participant's randomization or screening failure.

**Treatment period:** Starts with the administration of the first dose of study treatment and ends on the day of the last dose of study treatment. The study participants will be treated for 12 weeks.

**Safety follow-up period:** Starts on the day after the last dose of study treatment and ends at the EOS visit ( $10 \pm 3$  days after EOT).

Participation in the study ends with the completion of the EOS visit [Table 1]. The duration of participation in the study of a study participant is expected to be up to 128 days.

The visit schedule and protocol-mandated procedures are performed according to the schedule of activities [Table 1] and are described in Section 7.2.

The overall study design is depicted in Figure 1.

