# 9.2.10 Specific safety endpoints

*Daytime sleepiness* is defined daily as any score > 3 on the SSS after taking the morning dose. It will be collected on Days 1–14 and expressed as a number of days per week (as for the primary efficacy outcome). A minimum of 7 diary entries are required, otherwise the data will be considered missing. The mean number of days with daytime sleepiness per week will be summarized by treatment group.

The number (%) of study participants with *suicidal ideation and/or behavior* based on the C-SSRS© will be tabulated by visit and treatment group.

*Withdrawal effects* will be described summarizing changes from changes from Week 12/EOT to EOS in BWSQ and HAMD-17 by treatment group.

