5.3.3 Medical history and concomitant diseases at screening

Relevant medical history and current medical conditions will be coded using MedDRA.

Any disease or diagnosis is defined as previous if 'Ongoing at informed consent' is answered as 'No'; all other diseases/diagnoses are considered as study concomitant (where answer is 'Yes').

Medical history and current (ongoing) medical conditions, excluding BED and BEDrelated symptoms, will be summarized separately, and listed. Summaries will be presented for each treatment group by primary SOC and PT. Medical history will be sorted by SOC and PT within each SOC by descending frequency based on all treatment groups combined.

ACT-539313		Statistical Analysis Plan
ID-082A201	Confidential	for Clinical Study Report
1 April 2022, page 18/60	Confidential	Version 3
		Doc No D-22 100

The MedDRA version used for reporting will be specified in the footnote of the applicable output.

5.3.4 **Previous and concomitant therapy**

Previous and concomitant therapies will be coded using the WHO Drug Global reference dictionary that employs the WHO ATC classification system. The WHO Drug Global version used for reporting will be specified in the footnote of the applicable output.

Previous therapies are any treatments for which the end date is prior to signing of the ICF. Any previous therapy is to be recorded in the 'Previous/Concomitant Medication' page if discontinued less than 30 days prior to signing of the informed consent form.

Study-concomitant therapies are any treatments that are either ongoing at the signing of informed consent or initiated during the time from the signing of informed consent up to EOS. The use of all study-concomitant therapies (including contraceptives and traditional and alternative medicines, e.g., plant-, animal-, or mineral-based medicines) is to be recorded in the 'Previous/Concomitant Medication' page.

Study treatment-concomitant therapies (a subset of study-concomitant therapies) are any treatments that are either ongoing at the start of study treatment or initiated during the study period until 1 day after the last dose of study treatment.

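### The Protocol's recording of concomitant therapy stops at the last dose, with no check at EOS, while the SAP tabulates therapies started up to EOS and withdrawal is assessed in that gap

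*Protocol*

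**What the plan says.** **Definition and recording duty.** Protocol 6.2 and 7.2.2 use the same definition: a concomitant medication or non-drug therapy "is any treatment that is either ongoing at the start of study treatment or is initiated during the treatment period". Section 7.2.2 attaches the eCRF recording duty to "The use of all concomitant medications / non-pharmacological therapy", so the duty reaches no further than the definition.

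**Periods.** Protocol 4.1.1 describes the treatment period as follows: "Starts with the administration of the first dose of study treatment and ends on the day of the last dose of study treatment". Of the safety follow-up it says: "Starts on the day after the last dose of study treatment and ends at the EOS visit". EOS is placed 10 ± 3 days after EOT.

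**Schedule.** In Table 1 the previous/concomitant therapy row has nine marks, Visit 1 to EOT, and none at EOS.

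**Ban.** Protocol 6.2.2 forbids CNS-active drugs, among them anxiolytics, antidepressants and sleep drugs, if "planned to be initiated during the study and until EOS".

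**Withdrawal.** Protocol 9.2.10 summarises "changes from Week 12/EOT to EOS in BWSQ and HAMD-17 by treatment group". SAP 7.7 adds the incidence of AEs in the safety follow-up period.

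**SAP.** Section 5.3.4 defines study-concomitant therapies as those ongoing at consent or "initiated during the time from the signing of informed consent up to EOS". It says that all of them belong on the eCRF medication page, and it plans a separate table for them.

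**The concern.** The Protocol stops asking about medication just where the withdrawal window opens. A participant with rebound anxiety or insomnia after the last dose may start a drug that relieves it, and such relief could lower the EOS scores on BWSQ and HAMD-17. Pharmacological withdrawal is expected only in the active arm, so unrecorded symptomatic treatment would tend to pull the comparison towards no difference. A reader of the summaries could not tell an absence of withdrawal from withdrawal that was treated.

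This matters somewhat more here than in a later trial. Protocol 2.2 and 2.4 report earlier multiple dosing for at most 10 days, in healthy subjects. This study is the first look at stopping after 12 weeks, and BWSQ is taken only at EOT and EOS.

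Two further consequences follow. Compliance with the ban after EOT has no scheduled check, and the SAP table of therapies up to EOS relies on data that the Protocol does not require sites to collect.

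**Working it through.** The plan states no figure on this point, so the check compares the end of each window.

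| Source | What it governs | Runs to |
|---|---|---|
| Protocol 6.2 and 7.2.2, with 4.1.1 | Latest start of a drug that must be recorded | Day of last dose |
| Table 1, previous/concomitant therapy | Scheduled medication check | EOT visit |
| Table 1, urine drug screen | Scheduled laboratory check | EOT visit |
| Protocol 6.2.2 | Ban on CNS-active drugs | EOS |
| SAP 5.3.4, study-concomitant therapies | Definition, recording, table | EOS |
| Protocol 9.2.10, SAP 7.7 | Withdrawal assessment | EOT to EOS |
| Protocol 8.2.1 | AE recording | EOS |

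1. **Length of the gap.** From the EOT visit to EOS: 10 − 3 = 7 days to 10 + 3 = 13 days. Neither a medication question nor a drug screen is scheduled after the EOT visit.
2. **Premature discontinuation.** The EOT visit falls 1 to 5 days after the last intake (Protocol 5.9.1). Last dose to EOS is then 1 + 7 = 8 to 5 + 13 = 18 days. The EOT visit carries a medication check, so the stretch without one is still 7 to 13 days. A drug first started between the last dose and that visit nevertheless falls outside the Protocol definition.
3. **What falls in the gap.** Drugs started on or before the last dose remain concomitant under the Protocol. Only drugs first started afterwards are outside it.
4. **Is the difference declared?** SAP 12.1 lists only a change of analysis set for demographics and disease characteristics. SAP 12.3 and 12.4 report nothing. The wider SAP window is therefore an undeclared departure from Protocol 6.2 and 7.2.2.
5. **Is there an analysis rule?** SAP 7.7 summarises changes in BWSQ and HAMD-17 to EOS without saying how CNS-active drug use in the interval will be shown.

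**The case against.** A reader might infer that drugs taken during withdrawal go unrecorded and that the ban cannot be checked at all. The documents do not support that much.

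- SAP 5.3.4 says therapies started up to EOS are to be recorded, and those related to an AE are flagged in the listing. The eCRF specifications that the SAP cites are not among the documents, so the page may well collect such drugs. This stands, and actual capture is unknown. But sites work from the Protocol and its schedule, and a SAP cannot create a collection duty.
- Partial routes exist. Medical or surgical interventions are documented at any time in the study (Protocol 7.2.2). Remote visits ask about new medication (Protocol 7.2.5.8). Forbidden medication is a deviation category (SAP 5.2). These soften the point without closing it: a self-started sleep aid is not clearly an intervention, the remote question is part of the COVID-19 provisions and is not a scheduled item at an on-site EOS, and a deviation must first be detected.
- AEs are asked about at each visit and recorded to EOS, and SAP 7.7.1 uses them as a withdrawal measure. Symptoms bad enough to be treated can still be counted there. This stands: the signal need not be lost. The AE form contents in Protocol 8.2.1, however, do not include treatment given for the event.

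A reader might also infer a numerical bias, or want the summaries repeated without the EOS scores of drug-takers. The documents give no rate of use and no size of effect. Nor would exclusion repair the mean. Let a fraction *m* of the active arm have a rise *r* that is fully masked, a fraction *u* have the same rise unmasked, and the rest have none. The unmasked truth is (*m* + *u*)*r*, the observed mean is *ur*, and after exclusion it is *ur*/(1 − *m*). For small *m* that is almost the observed value. Exclusion also selects on an event after randomisation and removes people who had withdrawal.

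**Conclusion.** The point holds as an unreconciled conflict between Protocol and SAP, together with a missing check at EOS. Under the Protocol, a drug first started after the last dose need not be recorded, and nothing is scheduled to detect it in the 7 to 13 days after the EOT visit. The CNS-active ban and the withdrawal assessment both cover that interval.

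Its reach is limited. The withdrawal summaries are descriptive, with no test or decision rule, and the primary efficacy analysis is untouched. The direction of any masking, towards no difference, rests on the assumption that withdrawal arises only in the active arm and that the drugs taken relieve what the scales measure. Its size cannot be estimated from the documents. The finding rests on the Protocol text and schedule, not on knowledge of what the eCRF collected. It is worth correcting because the correction is cheap and makes the withdrawal results interpretable.

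**What to change.** - **Protocol Table 1:** mark previous/concomitant therapy at EOS.
- **Protocol 6.2 and 7.2.2:** extend the recording definition to therapies started up to EOS, to match SAP 5.3.4. The ban itself is not altered.
- **SAP section 12:** declare that the SAP window is wider than that of Protocol Version 3.
- **SAP 7.7:** report, by arm, the number of participants who started a CNS-active drug between last dose and EOS, and flag them in the BWSQ and HAMD-17 listings. Keep their EOS scores in the summaries.

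The cost is one question at a visit that already takes place and one extra summary line, with no new visit or procedure. For participants already past EOS the Protocol change recovers nothing. For them the study report should say that recording of drugs started after the last dose was not required by the Protocol, and whether the eCRF collected them.
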